7.9 Adverse events

Individual listings of adverse events (including age, gender, adverse event as reported, time to adverse event after study drug intake, duration, intensity, relation to study drug, action taken and outcome) will be provided.

7.9.1 Definitions

7.9.1.1 Adverse event (AE)

An AE is any untoward medical occurrence in a subject administered with a pharmaceutical product and does not necessarily have to have a causal relationship with this treatment. An AE can therefore be any unfavorable and unintended sign (including an abnormal laboratory finding), symptom, or disease temporally associated with the use of a drug, whether or not considered related to the drug. AE associated with the use of a drug, whether or not considered drug related, includes AE occurring in the course of the use of a drug, from an overdose whether accidental or intentional, from drug abuse, from drug withdrawal, or if there is a reasonable possibility that the event occurred purely as a result of participation in the study, even if it is not related to the drug.

The clinical manifestation of any failure of expected pharmacological action is not recorded as an AE, if it is already reflected as an outcome captured in the eCRF, except if the event fulfills the criteria for a “serious” AE.

A surgical procedure or intervention that was planned prior to visit 2 should not be recorded as an AE. Conditions, including abnormal physical examination findings, symptoms, and diseases will be recorded as medical history if they started before visit 2 and no symptoms or treatment are present until visit 2, or symptoms or treatment are present after visit 2 at unchanged intensity.

If the condition started or deteriorated after administration of study drug at visit 2, it will be documented as adverse event.

7.9.1.2 Serious adverse event (SAE)

An SAE is any untoward medical occurrence that at any dose is resulting in death, is life-threatening (i.e. the patient was at risk of death at the time of the event), requires hospitalization or prolongation of existing hospitalization unless the admission results in a hospital stay of less than 12 hours, is pre-planned, or is not associated with an AE (i.e. social hospitalization for purposes of respite care), results in persistent or significant disability/incapacity. In addition, SAE is a congenital anomaly or a birth defect or an important medical event, including associated invasive treatment, as judged by the investigator. For reporting of a SAE, local regulations take precedence if more stringent definitions are applicable.

7.9.1.3 Unexpected AEs

An unexpected AE is any adverse drug event whose specificity or severity is not consistent with the investigator brochure (or package inserts for marketed products). Also, reports which add significant information on specificity or severity of an already documented AE constitute unexpected AEs. For example, an event more specific or more severe than described in the investigator brochure would be considered "unexpected".

Specific examples: 1) acute renal failure as a labeled adverse event with a subsequent new report of interstitial nephritis and 2) hepatitis with a first report of fulminant hepatitis.

7.9.2 Relationship of AE to the study drug

The assessment of the causal relationship between an AE and the use of medication is a clinical decision based on all available information at the time of the completion of the eCRF and is based on whether there was a "reasonable causal relationship" to the medication.

An assessment of "no" would include the existence of a clear alternative explanation, e.g. mechanical bleeding at surgical site, or non-plausibility. An assessment of "yes" indicates that there is a reasonable suspicion that the AE is associated with the use of the drug. Factors in assessing the relationship of the AE to study treatment include the temporal sequence from drug administration (the event should occur after the drug is given) and the length of time from drug exposure, recovery on drug discontinuation (de-challenge), and recurrence on drug re-introduction (re-challenge), underlying, concomitant, or intercurrent diseases should be evaluated in the context of the natural history and course of any disease the child may have, concomitant medication or treatment and, finally, the pharmacology and pharmacokinetics of study treatment.

7.9.3 Causal relationship to protocol-required procedures

The assessment of a possible causal relationship between the AE and protocol-required procedures is based on the question whether there was a "reasonable causal relationship" to protocol-required procedure(s). Possible answers are "yes" or "no".

7.9.4 Intensity of an AE, action taken and outcome

The intensity of an AE is assessed as mild (usually transient in nature and generally not interfering with normal activities), moderate (sufficiently discomforting to interfere with normal activities), or severe (prevents normal activities).

Any action on study treatment to resolve the AE is to be documented as either: study drug withdrawn, interrupted, dose not changed, not applicable or unknown. Other specific treatment(s) of AEs will be documented as: none, remedial drug therapy or other. The outcome of the AE is to be documented as: recovered/resolved, recovering/resolving, recovered/resolved with sequelae, not recovered/not resolved, fatal or unknown.

7.9.5 Assessments and documentation of adverse events

Complications that occur during the screening period between visit 1 and visit 2 will not be reported as AEs, because no study medication or study related procedures are required during this period, but may be documented in the medical history, if applicable.

After study drug intake at visit 2, documentation of AEs must be supported by an entry in the subject's file. A laboratory test abnormality considered clinically relevant, e.g. causing the subject to withdraw from the study, requiring treatment or causing apparent clinical manifestations, or judged relevant by the investigator, should be reported as an AE. Each event should be described in detail along with start and stop dates, severity, relationship to study drug, action taken and outcome.

When assigning the cause of death, "death" should not be recorded as an AE on the AE page. Instead, "death" is the outcome of underlying AE(s).

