Dispense study medication Instruct how to administer the study medication Provide study booklet Provide rivaroxaban oral suspension handling guidelines		• ^c			
Record all concomitant medication		•	•	•	•
Collect baseline imaging ^d	•				
Repeat ultrasound imaging ^d		•		• ^e	
Check for study outcomes ^d			•	•	•
Check adverse events		•	•	•	•
Check drug accountability and compliance				•	
Check if anticoagulant treatment continued after Visit 4					•
Complete eCRF	•	•	•	•	•

ALT = alanine aminotransferase, eCRF = electronic case report form, Hb = hemoglobin; INR= international normalized ratio, VKA= vitamin K antagonist

^a The screening visit can be performed up to 10 days prior to inclusion into the study.

^b Hb, platelets, creatinine, ALT, total and direct bilirubin results should be available within 10 days prior to inclusion into the study. If results are not available, obtain blood sample.

^c If child discharged from the hospital.

^d Compile adjudication package and send it to the adjudication office.

^e Repeat ultrasound can be obtained on Day 8 ± 1.

^f INR should be below 2.5 before starting rivaroxaban (see Section 5.1.1.3).

¹⁶ The study flow chart was modified via Amendment 1 (see Section 16.1.2.1)

Table 2: Flow chart: pharmacokinetics and pharmacodynamics ¹⁷

PK and PD ^a	Visit 1	Visit 2			Treatment day 2			Visit 3			Treatment day 4 to 7			Visit 4
Rivaroxaban treatment days	Screen day -10 to day 1	Treatment day 1			Treatment day 2			Treatment day 3			Treatment day 4 to 7			Day 8
Rivaroxaban administration		1 st dose	2 nd dose	3 rd dose	1 st dose	2 nd dose	3 rd dose	1 st dose	2 nd dose	3 rd dose	1 st dose	2 nd dose	3 rd dose	
PK/PD time points		0.5 to 3 hr post dose	7 to 8hr post dose					0.5 to 3 hr post dose	7 to 8hr post dose					10-16 hr after last dose at day 7
Obtain blood sample for PK ^b		•	•					•	•					
Obtain blood sample for PD ^c			•					•						• ^d

hr = hour(s), PD = pharmacodynamics, PK = pharmacokinetics
^a The approximate total blood volume taken per child for PK/PD is 6.6 mL. Always draw the PD sample as the last sample.
^b Blood volume per PK sample is approximately 0.6 mL; total blood volume for all PK samples is 2.4 mL.
^c Blood volume per PD sample is approximately 1.4 mL; total blood volume for all PD samples is 4.2 mL.
^d If continued treatment with anticoagulants is necessary, administer the anticoagulant after last sample is taken for rivaroxaban.

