5.1.1.1 Switching from heparin to rivaroxaban

If the child received heparin treatment before enrollment, enrollment should be planned 4 hours after stopping the infusion of UFH, 6 - 12 hours after the last injection of LMWH with a twice-daily regimen, 12 - 24 hours after the last injection of LMWH with a once-daily

³² The dosing table was added via Amendment 1 (see Section [16.1.2.4](#))

regimen. Heparin treatment cannot be continued after the start of rivaroxaban treatment in these children.

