5.1.1.3 Switching from VKA to rivaroxaban - amended

If a child is on VKA therapy and has a supra-therapeutic INR (> 3.0), enrollment into the study should be delayed. In case of an INR between 2.5 to 3.0, enrollment can be done and the first rivaroxaban dose should be delayed to the next day. If the INR is below 2.5, enrollment can be done and the first rivaroxaban dose can be taken on the day of enrollment. VKA therapy cannot be continued after enrollment.

Children who switch from VKA to rivaroxaban should avoid using both drugs at therapeutic doses simultaneously. Rivaroxaban can be started only if the INR is < 2.5 .³³

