7.9.6 Reporting of serious adverse events

All investigators will be thoroughly instructed and trained on all relevant aspects of the reporting obligations for SAEs. This information, including all relevant contact details, is summarized in the investigator site file and will be updated as needed.

SAEs occurring after study drug intake at visit 2 until 1 month after the last dose must be reported within 24 hours of the investigator's awareness. Reports should be as complete as possible, and must be followed up until resolution or stabilization. When required, and according to local law and regulations, SAEs must be reported to the ethics committee and regulatory authorities.

If reported, SAEs occurring after the protocol-defined observation period will be processed by Bayer according to all applicable regulations.

Bayer will inform all investigational sites about the occurrence of suspected unexpected serious adverse reactions (SUSARs) according to all applicable regulations.

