7.9.7 Study specific exceptions to the (S)AE reporting

AEs between visit 1 and visit 2 will not need to be reported. The efficacy outcomes (symptomatic recurrent thromboembolism and asymptomatic deterioration in thrombotic burden on repeat imaging) will not be reported as (S)AE. Transfer of children to a rehabilitation unit as a standard practice will not be considered as a prolonged hospitalization and should not be reported as a SAE. However, if this transfer is part of treatment of a medical complication, it should be considered as prolonged hospitalization and the event should be reported as a SAE. To collect additional information about clinically important laboratory abnormalities, any laboratory abnormality that required cessation of the study drug will be captured as a SAE.

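### The reason given for not reporting events before visit 2 conflicts with other sections, and events tied to study steps before the first dose have no AE/SAE route

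*Protocol*

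**What the plan says.** **Exemption.** Protocol 7.9.5 does not treat complications between visit 1 and visit 2 as AEs, "because no study medication or study related procedures are required during this period". It adds that they are not reported "but may be documented in the medical history, if applicable". Section 7.9.7 repeats the rule: "AEs between visit 1 and visit 2 will not need to be reported". Section 6.2 says the same.

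**Start of documentation.** Section 7.9.1.1 makes a condition an AE if it begins or worsens after study drug is given at visit 2. Section 7.9.5 ties AE documentation to drug intake at visit 2. For SAEs, 7.9.6 says: "SAEs occurring after study drug intake at visit 2 until 1 month after the last dose must be reported within 24 hours".

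**Study steps before the first dose.**
- Section 5.1.1.1, children on UFH: "enrollment should be planned 4 hours after stopping the infusion of UFH". Table 1 places enrolment at visit 2.
- Table 1 footnote b, attached to the laboratory check in the visit 1 column: "If results are not available, obtain blood sample". Section 6.3 repeats this fallback under visit 2, whereas 6.2 says no sample need be drawn for screening because routine results will exist.
- Section 5.1.1.3, children on VKA with an INR of 2.5 to 3.0: "enrollment can be done and the first rivaroxaban dose should be delayed to the next day". VKA may not continue after enrolment.

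**What should count.** The AE definition in 7.9.1.1 reaches events where there is a "reasonable possibility that the event occurred purely as a result of participation in the study", even if unrelated to the drug. Section 7.9.3 asks for causality to protocol-required procedures.

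**The concern.** A rule that switches off AE reporting because nothing study-related happens is sound only if nothing study-related happens. Here the protocol sets when a continuous heparin infusion must have ended and keeps a blood draw in reserve, both after consent and before the first dose.

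The AE definition and the procedure-causality question are meant to catch harm that comes from taking part rather than from the drug. Tying the start of documentation to drug intake removes the pre-dose events of that kind. Such an event would have no 24-hour report and no causality assessment. In infants with documented thrombosis, in a study planned for at least eight children, one such event would matter to anyone judging what entry into the trial involves.

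**Working it through.** No figure in the plan is at issue, so the check sets the sections side by side and follows four kinds of event.

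**1. Does the reason in 7.9.5 hold for visit 1 to visit 2?**
- Consent precedes screening (6.2), so these children are already participants.
- UFH: enrolment is at visit 2 and is planned 4 hours after the stop, so the stop precedes enrolment. This is a study-timed break in a continuous infusion, and it conflicts with the stated reason.
- Laboratory sample: footnote b sits in the visit 1 column and asks for a draw when results are missing. This also conflicts with the reason, but only conditionally. Section 6.2 says no screening sample is needed and 6.3 puts the fallback at visit 2, so the three places do not agree with each other.
- Low molecular weight heparin (LMWH): the windows are 6-12 hours (twice daily) and 12-24 hours (once daily) after the last injection. If the usual intervals are about 12 and 24 hours (an assumption), these windows lie within one dosing interval and add no extra gap.
- VKA stop and INR draw: both belong to enrolment or visit 2, so they fall outside the period that the reason covers and do not contradict it.

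**2. Where would a pre-dose event be recorded?**

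| Event | AE/SAE route | Other route |
|---|---|---|
| After the UFH stop, before enrolment | None (6.2, 7.9.5, 7.9.7) | Optional medical history; the ultrasound before the first dose, if the child gets that far. Adjudication covers only events after visit 2 (6.14.2) |
| From a fallback blood draw at screening | None (same sections) | Optional medical history |
| Between enrolment and a next-day first dose (VKA, INR 2.5-3.0) | None: not after drug intake (7.9.1.1, 7.9.5, 7.9.6) | Adjudication of suspected thrombotic or bleeding events, other vascular events and deaths |
| SAE in an enrolled child who is never dosed | None: 7.9.6 runs from drug intake to 1 month after the last dose | Contact at the end of the treatment period (3.1); adjudication as above |

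The third row does not depend on which day is called visit 2. If it is the enrolment day, the event is later than the screening exemption, later than the 7.9.1.1 medical-history rule (conditions that began before visit 2) and earlier than drug intake. If it is the first-dose day, the screening exemption applies. Neither reading gives an AE route.

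**3. Does the visit 2 AE check close the gap?** Table 1 and 6.3 list an AE check at visit 2. What it may record is governed by 7.9.1.1 and 7.9.5, which begin at drug intake, so it does not.

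**4. Would a new start date be enough for thrombotic events?** No. Section 7.9.7 keeps symptomatic recurrence and asymptomatic deterioration out of (S)AE reporting even on drug, because they go to adjudication as outcomes. Before visit 2 there is no adjudication route, so that exemption must be dealt with explicitly.

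**The case against.** The strongest reply is that this is a wording slip with little consequence, and several parts of it stand.

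- **Blood draws.** A reader might infer that the protocol requires pre-dose sampling in every child. It does not. The laboratory draw is a fallback, 6.2 says none is needed, and the INR draw applies only to children on VKA, at visit 2.
- **Prior anticoagulation.** A reader might infer that all children are left uncovered during the switch. Only the UFH stop clearly falls inside the exempt period. The LMWH windows are probably ordinary intervals. A child on VKA at INR 2.5-3.0 is at or above the target of 2.5 given in Section 1, which also describes slow offset.
- **No record at all.** A reader might infer that such events vanish. Medical history is checked again at visit 2. The pre-dose ultrasound goes to adjudication. The adjudication committee covers suspected events after visit 2 whether or not the child was dosed. The data monitoring committee (DMC) reviews recurrent thromboembolism and bleeding directly. The full analysis set includes all consented children, and SAP 4.1 lists those not dosed.
- **Thrombus progression.** Its absence from SAE reporting is due in part to 7.9.7, not only to the start rule.
- **Background events.** Collecting every SAE from consent would mostly add events from underlying disease.

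What remains is that medical history is optional and carries no causality question or 24-hour duty, and that adjudication starts after visit 2 and covers outcome events only. None of these replaces an AE/SAE route for harm from a study step.

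**Conclusion.** The point holds in two parts. First, the reason in 7.9.5 is inconsistent with 5.1.1.1 and Table 1 footnote b; footnote b and 6.3 must also be reconciled with 6.2. Second, because documentation begins at drug intake, events related to study steps before the first dose, and SAEs in enrolled children never dosed, have no AE/SAE route and no procedure-causality assessment.

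The exposed time is short: 4 hours for UFH, and until the next day for the VKA case. The documents give no event rate for these intervals. Expressing them as a share of the treatment week would not measure risk. Sample size, PK/PD results and on-drug bleeding incidence are untouched.

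Two assumptions matter. The LMWH reading assumes injection intervals of about 12 and 24 hours. The UFH conflict takes visit 2 to begin at enrolment. If the whole of day 1 counted as visit 2, the stop could fall on that day. The conflict with the stated reason would then weaken, but the gap before first intake would remain. The switching rules themselves are not judged here.

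**What to change.** 1. Delete or correct the reason in 7.9.5, and reconcile Table 1 footnote b and 6.3 with 6.2 on whether and when a laboratory sample is drawn.
2. In 6.2 and 7.9.5 to 7.9.7, collect from informed consent to first dose any AE or SAE judged related to a protocol-required procedure or to stopping prior anticoagulation for study entry. Apply the 24-hour rule to these SAEs, and include enrolled children who are never dosed. Limiting collection to related events avoids a load of background SAEs.
3. State that the 7.9.7 exemption for thromboembolic outcomes does not apply before the first dose, or send such events to the adjudication committee and the DMC.
4. List these events separately as pre-treatment in the SAP, leaving the on-drug bleeding incidence as planned.

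The cost is protocol wording, an AE form open from consent, and a few more forms and listings. No switching rule and no planned analysis changes.

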7.9.6 Reporting of serious adverse events

All investigators will be thoroughly instructed and trained on all relevant aspects of the reporting obligations for SAEs. This information, including all relevant contact details, is summarized in the investigator site file and will be updated as needed.

SAEs occurring after study drug intake at visit 2 until 1 month after the last dose must be reported within 24 hours of the investigator's awareness. Reports should be as complete as possible, and must be followed up until resolution or stabilization. When required, and according to local law and regulations, SAEs must be reported to the ethics committee and regulatory authorities.

If reported, SAEs occurring after the protocol-defined observation period will be processed by Bayer according to all applicable regulations.

Bayer will inform all investigational sites about the occurrence of suspected unexpected serious adverse reactions (SUSARs) according to all applicable regulations.

7.9.7 Study specific exceptions to the (S)AE reporting

AEs between visit 1 and visit 2 will not need to be reported. The efficacy outcomes (symptomatic recurrent thromboembolism and asymptomatic deterioration in thrombotic burden on repeat imaging) will not be reported as (S)AE. Transfer of children to a rehabilitation unit as a standard practice will not be considered as a prolonged hospitalization and should not be reported as a SAE. However, if this transfer is part of treatment of a medical complication, it should be considered as prolonged hospitalization and the event should be reported as a SAE. To collect additional information about clinically important laboratory abnormalities, any laboratory abnormality that required cessation of the study drug will be captured as a SAE.

7.9.8 Expected AEs

The applicable reference document is the most current version of the investigator's brochure (IB) / Company Core Data Sheet (CCDS). Overview listings of frequent events that have occurred so far in the clinical development are shown in the current IB. If relevant new safety information is identified, it will be integrated into an update of the IB and distributed. The expectedness of AEs will be determined by Bayer according to the applicable reference document and according to all local regulations.

7.9.9 Adverse events of special safety interest

The following AEs are considered as AEs of special safety interest:

- Concurrent elevations of alanine aminotransferase (ALT) > 5x ULN and total bilirubin > 2x ULN with direct bilirubin > 20% of the total.
- A platelet count below $100 \times 10^9/L$.
- Allergic skin reactions, allergic systemic reactions

7.10 Premature discontinuation of study medication

Children prematurely discontinue study medication

- at the request of parents/legal representative without the need to provide a reason.
- if, in the investigator's opinion, study medication should be stopped for any reason.
- In case of symptomatic efficacy outcome for which anticoagulant or fibrinolytic therapy is indicated.
- at the (exceptional) request of Bayer.

If study medication is temporarily discontinued, it can be restarted as long as the total treatment duration does not exceed the intended 7-day treatment period. If study medication is permanently discontinued, further treatment is at the investigator's discretion.

If parents/legal representative indicate to stop study medication, the investigator will ask to continue with study visits as planned, only with the aim to collect potential study outcomes and AEs. If parents/legal representative indicate that they no longer authorize the investigator to continue to obtain outcome data, this will be respected and documented in the source records.

In all children who prematurely discontinue study treatment for other reasons than withdrawal of the informed consent, study visits will take place as planned only with the reason to collect potential study outcomes and AEs. A special effort will be made to collect data from children who did not complete all study visits.

